9.2.4 Efficacy Analyses for Additional Endpoints

Additional efficacy analysis includes the following endpoints at the scheduled time points in Section 5.2 other than those specified for the primary and key secondary variables:

- Proportion of subjects with no radiographic progression is defined as
 - change from baseline in SHS \leq 0;
 - change from baseline in SHS \leq 0.5.
- Change from baseline in joint space narrowing score and joint erosion score.
- Change from baseline in individual components of ACR response
 - Change from baseline in Tender Joint Count (TJC) (0-68);
 - \circ Change from baseline in Swollen Joint Count (SJC) (0-66);
 - Change from baseline in Physician Global Assessment (PGA) Disease Activity (NRS);
 - Change from baseline in Patient's Global Assessment (PtGA) Disease Activity (NRS);
 - Change from baseline in Patient's Assessment of Pain Numerical Rating Scale (NRS);

- Change from baseline in Health Assessment Questionnaire Disability Index (HAQ-DI);
- Change from baseline in High-Sensitivity C Reactive Protein (hs-CRP);
- ACR 20/50/70 response rates;
- Proportion of subjects achieving MDA;
- Change from baseline in Leeds Dactylitis Index (LDI) (for subjects with baseline LDI > 0);
- Change from baseline in dactylitis count (for subjects with baseline LDI > 0);
- Proportion of subjects with resolution of dactylitis (for subjects with baseline LDI > 0);
- Change from baseline in LEI (for subjects with baseline LEI > 0);
- Proportion of subjects with resolution of enthesitis defined as LEI = 0 (for subjects with baseline LEI > 0);
- Change from baseline in SPARCC Enthesitis Index (for subjects with baseline SPARCC Enthesitis Index > 0);
- Proportion of subjects with resolution of enthesitis defined as SPARCC Enthesitis Index = 0 (for subjects with baseline SPARCC Enthesitis Index > 0);
- Change from baseline in total enthesitis count (for subjects with baseline total enthesitis count > 0);
- Proportion of subjects with resolution of enthesitis defined as total enthesitis count = 0 (for subjects with baseline total enthesitis count > 0);
- PASI 75/90/100 response rates (for subjects with ≥ 3% Body Surface Area (BSA) psoriasis at baseline);
- Proportion of subjects achieving a static Investigator Global Assessment of psoriasis (sIGA) score of 0 or 1 and at least a 2-point improvement from baseline (for subjects with baseline sIGA ≥ 2);
- Change from baseline in BSA-Ps (for subjects with baseline BSA-Ps > 0);
- Modified Psoriatic Arthritis Response Criteria (PsARC) response rate;
- Change from baseline in Disease Activity Score 28 (DAS28) (CRP);
- Change from baseline in DAS28 (ESR);

- Change from baseline in PsA Disease Activity Score (PASDAS);
- Change from baseline in Disease Activity In Psoriatic Arthritis (DAPSA) score;
- Change from baseline in Short Form 36 (SF-36) Health;
- Change from baseline in Functional Assessment of Chronic Illness Therapy (FACIT)-Fatigue;
- Change from baseline in EuroQol-5D-5L (EQ-5D-5L) index and VAS score;
- Change from baseline in Work Productivity and Activity Impairment (WPAI);
- Cumulative Health Resource Utilization (HRU);
- Change from baseline in Self-Assessment of Psoriasis Symptoms (SAPS);
- Change from baseline in Bath Ankylosing Spondylitis Disease Activity Index (BASDAI) (out of subjects with presence of psoriatic spondylitis at baseline);
- BASDAI 50 response rates (out of subjects with presence of psoriatic spondylitis at baseline);
- Change from baseline in Morning stiffness (mean of BASDAI Questions 5 and 6):
- Change from baseline in Morning stiffness severity 0 10 (BASDAI Question 5)
- Change from baseline in Morning stiffness duration 0 10 (BASDAI Question 6)
- Change from baseline in Ankylosing Spondylitis Disease Activity Score (ASDAS) (out of subjects with presence of psoriatic spondylitis at baseline);
- Proportion of subjects with ASDAS Inactive Disease (out of subjects with presence of psoriatic spondylitis at baseline);
- Proportion of subjects with ASDAS Major Improvement (out of subjects with presence of psoriatic spondylitis at baseline);
- Proportion of subjects with ASDAS Clinically Important Improvement (out of subjects with presence of psoriatic spondylitis at baseline);
- Proportion of subjects achieving a clinically meaningful improvement in HAQ-DI (≥ 0.35).

[figure not shown]

Non Radiographic Endpoints

For binary endpoints, frequencies and percentages will be reported for each treatment group. NRI will be used for primary analysis. For enthesitis and dactylitis related endpoints at Week 24, in addition to the NRI data handling as defined in Section 9.1.2, subjects who meet the rescue criteria (i.e., not achieving at least 20% improvement in either or both tender joint count (TJC) and swollen joint count (SJC) at both Week 12 and Week 16) will also be treated as non-responders. AO will be used as supplementary analysis. Point estimate and 95% CI using normal approximation will be provided for the response rate for each randomized treatment group. Treatment comparisons will be made between each upadacitinib dose to the combined placebo group and to the adalimumab group using the CMH (refer to Appendix A) test adjusting for the main stratification factor of current DMARD use (yes/no). Point estimate, 95% CI using normal approximation and the nominal p-value for the treatment difference will be presented.

For non-radiographic continuous endpoints, the LS mean and 95% CI for each randomized treatment group and the LS mean treatment difference, the associated 95% CI and the p-value between each upadacitinib dose group to the combined placebo group and to the adalimumab group will be provided using MMRM model as described in Section 9.1.2, with fixed effects of treatment, visit, treatment-by-visit interaction, the stratification factor of current DMARD use (yes/no) and the continuous fixed covariates of baseline measurement. The nominal p-value will be provided. For enthesitis and dactylitis related endpoints at Week 24, exploratory analysis accounting for potential influential outliers may be performed.

For change from baseline in each of the seven ACR components, the ANCOVA model using AO data handling as described in Section 9.2.3 will be conducted as supplementary analysis, with treatment and the stratification factor of current DMARD use (yes/no) as the fixed factors and the corresponding baseline values as the covariates. Nominal p-values will be provided.

Radiographic Endpoints

For proportion of subjects with no radiographic progression at Week 24, point estimate and 95% CI of the response rate for each randomized treatment group will be provided. Comparisons will be made between the upadacitinib 15 mg QD and 30 mg QD group and the combined placebo group using the CMH (refer to Appendix A) test adjusting for current DMARD use (yes/no). Point estimate, 95% CI and nominal p-value for the treatment comparison will be presented. Non-progression will be derived using both linear extrapolation imputation and AO.

[figure not shown]
For change from baseline in joint space narrowing score and joint erosion score at Week 24, linear extrapolation analysis and AO analysis will be performed similarly as described in Section 9.2.3.

In the linear extrapolation analysis for Week 56 radiographic endpoints, the missing Week 56 data will be imputed via linear extrapolation using available post-baseline x-ray data in the latest analysis window prior to Week 56. For placebo subjects who switched to upadacitinib at Week 24, their Week 56 x-ray data will be imputed via linear extrapolation using Week 24 x-ray data. In the AO analysis, the observed Week 56 measurements will be used regardless of treatment switching. Similar statistical inference approach as Week 24 analysis by original randomized treatment group will be used.

Nominal p-values will be provided.

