5.2.1 Inclusion Criteria

- 1. Adult male or female, at least \geq 18 years old at Screening.
- 2. Clinical diagnosis of PsA with symptom onset at least 6 months prior to the Screening Visit and fulfillment of the Classification Criteria for PsA (CASPAR) criteria.
- Subject has active disease at Baseline defined as ≥ 3 tender joints (based on 68 joint counts) and ≥ 3 swollen joints (based on 66 joint counts) at Screening and Baseline Visits.
- 4. Presence of either at Screening:
 - ≥ 1 erosion on x-ray as determined by central imaging review or;
 - hs-CRP > laboratory defined upper limit of normal (ULN).
- 5. Diagnosis of active plaque psoriasis or documented history of plaque psoriasis.
- 6. Subject has had an inadequate response (lack of efficacy after a minimum 12 week duration of therapy) to previous or current treatment with at least 1 non-biologic DMARD at maximally tolerated dose or up to dose defined in Inclusion Criterion 7 [(inadequate response to MTX is defined as ≥ 15 to ≤ 25 mg/week; or ≥ 10 mg/week in subjects who are intolerant of MTX at doses ≥ 12.5 mg/week after complete titration; for subjects in China, South Korea, Malaysia, Singapore, Hong Kong (China), Taiwan, and Japan inadequate response to MTX is defined as ≥ 7.5 mg/week), SSZ, LEF, cyclosporine, apremilast, bucillamine or iguratimod], or subject has an intolerance to or contraindication for DMARDs as defined by the investigator.
- 7. Subject who is on current treatment with concomitant non-biologic DMARDs at study entry must be on ≤ 2 non-biologic DMARDs (except the combination of

[figure not shown]
MTX and leflunomide) at the following doses: MTX (\leq 25 mg/week), SSZ (\leq 3000 mg/day), leflunomide (LEF) (\leq 20 mg/day), apremilast (\leq 60 mg/day), HCQ (\leq 400 mg/day), bucillamine (\leq 300 mg/day) and iguratimod (\leq 50 mg/day) for \geq 12 weeks and at stable dose for \geq 4 weeks prior to the Baseline Visit. No other DMARDs are permitted during the study. Use of MTX in combination with LEF is prohibited. Subjects who need to discontinue DMARDs prior to the Baseline Visit to comply with this inclusion criterion must follow the procedure specified below or at least five times the mean terminal elimination half-life of a drug:

- \geq 8 weeks for LEF if no elimination procedure was followed, or adhere to an elimination procedure (i.e., 11 days with cholestyramine, or 30 days washout with activated charcoal or as per local label);
- \geq 4 weeks for all others.

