5.0 Analysis Populations and Analysis Windows

5.1 Analysis Populations

Full Analysis Set (FAS)

The Full Analysis Set (FAS) includes all randomized subjects who received at least one dose of study drug. The FAS will be used for all efficacy and baseline analyses.

Per Protocol Analysis Set

The Per Protocol Analysis Set represents a subset of the FAS and consists of all FAS subjects who did not meet any major protocol deviations that are determined to have a potential impact on the primary efficacy endpoint up to Week 12 in Period 1 of the study. Additional analysis of the primary efficacy endpoint will be conducted on the Per Protocol analysis set, in order to evaluate the impact of major protocol deviations.

Protocol deviations with potential to affect the primary efficacy endpoint (key ICH deviations and other clinically significant non-ICH deviations) will be identified prior to the Week 24 database lock.

Safety Analysis Set

The Safety Analysis Set consists of all subjects who received at least one dose of study drug. For the Safety Analysis Set, subjects will be analyzed "as treated," regardless of the treatment randomized. "As treated" is determined by the treatment the subject received during the majority of the subject's drug exposure time in the analysis period.

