9.0 Efficacy Analysis

9.1 General Considerations

There are two sets of planned efficacy analysis: efficacy analysis through Week 24 and long-term efficacy analysis. Unless otherwise noted, all efficacy analyses will be carried out using the FAS population.

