9.4.9 Disability Index of Health Assessment Questionnaire (HAQ DI)

HAQ-DI is a self-reported patient outcome measurement. It is calculated as the mean of the scores from 8 following categories with a range 0-3: Dressing and Grooming, Rising, Eating, Walking, Hygiene, Reach, Grip, and Activities. Higher scores reflect greater disability.

The maximum score for all the questions in each category is considered as the score for the category. The HAQ-DI takes into account the subject's use of aids or devices or assistance in the scoring algorithm for a disability category. For each of the eight disability categories there is an AIDS OR DEVICES companion variable(s) that is used to record the type of assistance, if any, a subject uses for his/her usual activities. If aids or devices and/or assistance from another person are checked for a disability category, the score for this category is set to 2 (much difficulty), if the original score is 0 (no difficulty) or 1 (some difficulty). The HAQ-DI is then calculated by summing the adjusted categories scores and dividing by the number of categories answered. The HAQ-DI cannot be calculated if the patient does not have scores for at least 6 categories.

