9.4.10 Static Investigator Global Assessment of Psoriasis (sIGA)

The sIGA is a 5 point score ranging from 0 to 4, based on the investigator's assessment of the average elevation, erythema, and scaling of all psoriatic lesions. The assessment is considered "static" which refers to the patients disease state at the time of the assessments, without comparison to any of the patient's previous disease states, whether at Baseline or at a previous visit. A lower score indicates less severe psoriasis (0 = clear, 1 = almost clear, 2 = mild, 3 = moderate and 4 = severe).

A binary clinical endpoint based on sIGA is considered in this study. It is the proportion of subjects achieving a sIGA score of 0 or 1 and at least a 2-point improvement from baseline. This endpoint is calculated among the subjects with baseline sIGA score ≥ 2 .

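### The HAQ-DI ≥ 0.35 responder endpoint counts subjects whose baseline is too low to respond; report it also in subjects with baseline HAQ-DI ≥ 0.35

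*SAP*

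**What the plan says.** The endpoint appears in SAP 9.2.4 as "Proportion of subjects achieving a clinically meaningful improvement in HAQ-DI (≥ 0.35"). SAP 9.3 lists it again for the long-term analysis. Neither entry, nor the footnote to SAP Table 1, nor Protocol 5.3.3.3, attaches a baseline condition.

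The default population therefore applies. SAP 9.1: "Unless otherwise noted, all efficacy analyses will be carried out using the FAS population". SAP 5.1: "The Full Analysis Set (FAS) includes all randomized subjects who received at least one dose of study drug".

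On the scale, SAP 9.4.9 says: "It is calculated as the mean of the scores from 8 following categories with a range 0-3", with higher scores meaning more disability. It adds: "The HAQ-DI is then calculated by summing the adjusted categories scores and dividing by the number of categories answered". At least six categories must be scored.

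Protocol 5.2.1 defines active disease by joint counts: "Subject has active disease at Baseline defined as ≥ 3 tender joints (based on 68 joint counts) and ≥ 3 swollen joints". An erosion or a raised hs-CRP is also needed. No criterion sets a minimum HAQ-DI.

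Other endpoints in SAP 9.2.4 do carry a baseline condition. For the sIGA endpoint, which needs a 2-point improvement, SAP 9.4.10 says: "This endpoint is calculated among the subjects with baseline sIGA score ≥ 2". For dactylitis, SAP 9.2.4 has: "Proportion of subjects with resolution of dactylitis (for subjects with baseline LDI > 0").

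Through Week 24, binary additional endpoints are analysed with non-responder imputation (As Observed as supplementary) and compared with placebo and with adalimumab using nominal p-values.

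**The concern.** An improvement of 0.35 is a fall of 0.35 on a scale that stops at 0. Anyone who starts below 0.35 cannot achieve it, whatever the treatment does. The entry criteria let such subjects in and the analysis keeps them in the denominator at every visit where they are counted.

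The reported percentage then mixes two things: how often treatment produces a meaningful functional gain, and how many subjects had enough disability at baseline to show one. A reader who takes the percentage as a measure of drug effect, or compares it with a trial that had a different baseline mix, cannot separate the two. The absolute difference between arms also shrinks, which matters most where the contrast is small, as it could be against adalimumab.

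**Working it through.** The documents give no rate, power or sample size for this endpoint, so there is no figure to reproduce.

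**Step 1: who cannot respond.** The score is a sum of category scores divided by the number of categories answered (SAP 9.4.9). Values below 0.35 are:
- 8 answered: 0, 0.125, 0.25
- 7 answered: 0, 0.143, 0.286
- 6 answered: 0, 0.167, 0.333

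The largest possible improvement equals the baseline value, so none of these subjects can reach 0.35.

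**Step 2: effect on the rates.** Let f be the share of the FAS with baseline below 0.35, equal across arms in expectation because of randomisation. Let p1 and p0 be the response rates among subjects able to respond.
- All-FAS rates: (1 - f)p1 and (1 - f)p0
- All-FAS difference: (1 - f)(p1 - p0)
- Rate ratio: p1/p0, unchanged
- If p1 = p0, the difference is 0 in either population, so the null test stays valid.

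**Step 3: illustration.** Arm sizes are from Protocol 5.1: 410 per upadacitinib group, and 205 + 205 = 410 for combined placebo. The rates of 60% vs 35% and the range of f are assumptions. z uses the unpooled standard error; the restricted analysis has 410(1 - f) subjects per arm.

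| f | All-FAS rates | All-FAS difference | z, all FAS | z, restricted |
|---|---|---|---|---|
| 5% | 57.0% vs 33.3% | 23.8 points | 7.04 | 7.22 |
| 10% | 54.0% vs 31.5% | 22.5 points | 6.69 | 7.02 |
| 15% | 51.0% vs 29.8% | 21.3 points | 6.35 | 6.83 |
| 20% | 48.0% vs 28.0% | 20.0 points | 6.03 | 6.62 |

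**Step 4: precision at f = 15%.**
- All FAS: SE = sqrt((0.51 × 0.49 + 0.2975 × 0.7025)/410) = 3.35 points; z = 21.25/3.35, about 6.35
- Restricted: SE = sqrt((0.60 × 0.40 + 0.35 × 0.65)/348.5) = 3.66 points; z = 25/3.66, about 6.83

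The restricted 95% interval is wider (half-width 1.96 × 3.66 = 7.2 points, against 1.96 × 3.35 = 6.6). Its z is larger because the difference is larger.

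**Step 5: a smaller contrast.** With assumed rates of 55% vs 45% and two-sided 0.05, power is 73.7% in all FAS against 77.7% restricted at f = 10%, and 64.8% against 72.7% at f = 20%.

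In As Observed long-term tables, f is the share among subjects evaluated at that visit, so it may change between visits. The documents give nothing from which to size this.

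**The case against.** The strongest reply is that this is a choice of estimand. The proportion of all treated subjects who gain at least 0.35 is a legitimate population quantity on the SAP's declared default population, and it favours no arm. That stands. A reader might infer that the all-FAS rates are wrong or biased, but the documents do not support that reading: the rates answer a different question.

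A reader might also infer that the SAP restricts every other threshold endpoint to subjects able to reach it and overlooks only this one. It does not. The BSA ≥ 3% condition for PASI, and the conditions of LEI, LDI or SPARCC above 0, mark presence of a disease domain. ASDAS Major Improvement needs a fall of 2.000 in a score that cannot go below 0, yet is limited only to subjects with psoriatic spondylitis, with no score floor. Only the sIGA condition is a true attainability rule, so the precedent is one endpoint.

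Timing also limits the remedy. SAP 11.1 records that the primary and Period 1 analyses were completed under version 3.0 and that version 4.0 governs only future long-term reporting. Replacing the denominator now, in a direction expected to enlarge differences, would be post hoc and would break the series across visits.

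Finally, the consequence is limited: function is tested in the ranked sequence through mean change in HAQ-DI with baseline as a covariate, which this denominator does not touch.

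These arguments rule out replacing the all-FAS result. They do not remove the case for showing the restricted one beside it.

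**Conclusion.** The point holds as a matter of interpretability and sensitivity for one additional endpoint. By construction, subjects with baseline HAQ-DI below 0.35 cannot respond, the plan does not exclude them, and rates and risk differences scale by (1 - f). Under the assumed 60% vs 35%, that costs 1.3 to 5.0 points of a 25-point difference for f between 5% and 20%. If no enrolled subject is below 0.35, it costs nothing. Both the rates and f are assumptions.

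It would be tempting to say that restricting also gains precision. It does not: at f = 15% the standard error rises from 3.35 to 3.66 points while z rises from 6.35 to 6.83, so the restricted analysis is more sensitive, not more precise. Nor does anything here reach the primary or ranked conclusions; this endpoint lies outside the graphical testing procedure and has nominal p-values only.

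**What to change.** In SAP 9.3, and in 9.2.4 for consistency, add an analysis of this endpoint for subjects with baseline HAQ-DI ≥ 0.35, on the model of the sIGA ≥ 2 condition. Keep the all-FAS analysis for continuity with tables already produced. Report the number of subjects below 0.35 in each arm, so that the reader can see f and move between the two versions. For Week 24 and Period 1 time points, label the restricted result as supplementary, since that reporting is complete.

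The condition uses a pre-randomisation variable, so comparisons between originally randomised groups remain randomised comparisons. The cost is one phrase, one program filter and one more table, with a smaller denominator and a slightly wider confidence interval in the restricted version.

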The supplementary analysis for ranked non-radiographic secondary continuous endpoints will be conducted using AO data handling and using the analysis of covariance (ANCOVA) model with treatment and the stratification factor of current DMARD use (yes/no) as the fixed factors and the corresponding baseline values as the covariates. The corresponding estimand is the difference in the mean change from baseline in the efficacy endpoints at the protocol defined time point regardless of treatment discontinuation or use of rescue medication, comparing each upadacitinib dose group vs placebo. The analysis will be conducted for those who are randomized, received study drug and have the efficacy measurement at the protocol defined time point.

For the key continuous endpoint change from baseline in HAQ-DI at Week 12, tipping point analysis will also be conducted using multiple imputation (MI) as additional supplementary analysis to explore various missing data assumptions including missing not at random (MNAR). Details of the tipping point analysis for continuous endpoints are outlined in Appendix D.

Radiographic Endpoints

For change from baseline in SHS at Week 24, statistical inference will be conducted using ANCOVA model and the associated data handling as described in Section 9.1.2 with treatment and the stratification factor of current DMARD use (yes/no) as the fixed factors and the corresponding baseline values as the covariates. The primary estimand for the x-ray assessment is the difference in the mean change from baseline in SHS score at Week 24, under the assumption that patients with missing data, including those due to

premature discontinuation of study drug or use of rescue medication, can have their measurements at Week 24 predicted using their SHS score from the baseline window and the Week 16 window. The comparison will be between each upadacitinib dose group vs placebo for patients randomized and treated with at least one dose of study drug.

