interaction in the model. The "group" option in PROC MIXED is used to allow for heterogeneity among treatment groups in the covariance structure. The coefficient for treatment-by-time interaction is used to estimate the difference in rate of progression (per 24 weeks) comparing upadacitinib and placebo. The rate of progression (per 24 weeks) for each group respectively is also estimated using the coefficients for time and treatment-by-time interaction. In case the random coefficient model does not converge, a simplified model may be explored by removing the random intercept or fitting a fixed-effect linear effect model.

Additionally, in the event that data severely deviates from the normal distribution, non-parametric analyses such as the ranked ANCOVA may be considered for treatment comparison.

[figure not shown]

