Note: The input dataset is in wide format. TRTP denotes the treatment group. &COVCON denotes baseline continuous covariates including baseline age, baseline BMI, duration of PsA diagnosis and baseline value of the endpoint of interest. &COVCAT denotes categorical covariates including current use of non-biologic DMARD, gender, race, and regions. WEEK_2, WEEK_4, WEEK_8, WEEK_12 denote the observed values at each visit. &SJ1and &SJ2 denote the shift parameters for the placebo group and upadacitinib 15 MG group respectively.

In cases where the shifted values are smaller than the minimum or larger than maximum value of the endpoint, (i.e., out of range), the minimum or maximum value of the endpoint is used in further analysis steps. For each pair of shift parameters, the SAS procedure PROC MIXED is used for ANCOVA analysis with Huber-White sandwich errors which includes the fixed effects of treatment, the stratification factor of current DMARD use and the continuous fixed covariate of baseline measurement on each of the multiple imputed datasets to obtain the results for each upadacitinib treatment group versus the placebo group comparison. These results will be aggregated using Rubin's method to get p-values.

If one pair of shift parameters are found to just reverse the study conclusion, in terms of p-value larger than 0.05 (the original p-value < 0.05), then the shift parameters are identified as the tipping point. The results for a grid of shift parameter combinations are provided in tabular format.

The SAS code example of the data imputation step for tipping point analysis using MI is provided above. The SAS code example for the analysis and results combination step using PROC MIXED and PROC MIANALYZE is as follows:

```
PROC MIXED DATA=ALL EMPIRICAL;
```

```
ODS OUTPUT LSMEANS=MIXEDLSMEANS DIFFS=DIFF;
    BY Shift1 Shift2 IMPUTATION;
    CLASS TRTP STRATA USUBJID;
    MODEL CHG = BASELINE TRTP STRATA / SOLUTION;
    LSMEANS TRTP / CL PDIFF DIFF;
    Repeated/subject = USUBJID;
RUN;
DATA DIFF1;
    SET DIFF;
    COMPARISON= TRTP||' VS '||LEFT( TRTP);
RUN;
PROC SORT DATA=DIFF1; BY COMPARISON Shift1 Shift2 IMPUTATION; RUN;
PROC MIANALYZE DATA=DIFF1;
    ODS OUTPUT PARAMETERESTIMATES=GROUP OUTPUT;
    BY comparison shift1 shift2;
    MODELEFFECTS ESTIMATE;
    STDERR STDERR;
RUN;
/* Comparison of "UPA 15 mg" vs. "Placebo" */
data miparm1;
set GROUP OUTPUT;
if comparison='1
                           VS

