                                          2' then output miparm1;
proc transpose data=miparm1 (keep= Shift1 Shift2 Probt)
out=wide miparm1;
by shift1;
id shift2;
var Probt;
run:
```

Note: The input dataset ALL includes all (# of shift1 parameters) * (# of shift2 parameters) * (# of imputations in MI) imputed datasets. TRTP denotes the treatment group and STRATA denotes the stratification factor used in analysis. CHG denotes the change from baseline value and BASELINE denotes the baseline value.

[figure not shown]
MI Analysis for Radiographic Continuous Endpoints

The MI analysis will impute missing data multiple times under appropriate random variation and thus generate multiple imputed "pseudo-complete" datasets. The imputation assumes of missing at random (MAR). ANCOVA will be performed on each of the multiple imputed datasets. The results will be aggregated across the multiple imputed datasets using Rubin's method. The SAS procedure PROC MI with the monotone

statement and REGRESSION method is used. Before applying PROC MI, MCMC is applied where necessary to augment data into monotone missing pattern. The SAS code example for PROC MI is as follows:

PROC MI DATA=DATA WIDE OUT=OUTMI NIMPUTE=1 SEED=12345;

[figure not shown]
```
Mcmc impute = monotone;
      VAR &COVCON base aval;
       By trtp;
RUN:
PROC MI DATA=DATA WIDE OUT=OUTMI NIMPUTE=20 SEED=12345;
      CLASS &COVCAT;
     MONOTONE;
      VAR &COVCON &COVCAT base aval;
       By trtp;
RUN:
       The input dataset is in wide format. TRTP denotes the treatment group. &COVCON denotes baseline
Note:
       continuous covariates including baseline age, baseline BMI, duration of PsA diagnosis and baseline value of
       the endpoint of interest. &COVCAT denotes categorical covariates including current use of non-biologic
       DMARD, gender, race and regions. WEEK 16, WEEK 24 denote the observed values at each visit.
PROC MIXED DATA=ALL;
    ODS OUTPUT LSMEANS=MIXEDLSMEANS DIFFS=DIFF;
    BY IMPUTATION ;
    CLASS TRTP STRATA;
    MODEL CHG = BASELINE TRTP STRATA / SOLUTION;
    LSMEANS TRTP / CL PDIFF DIFF;
RUN:
DATA DIFF1;
    SET DIFF;
    COMPARISON= TRTP||' VS '||LEFT( TRTP);
RUN;
PROC SORT DATA=DIFF1; BY COMPARISON IMPUTATION ; RUN;
PROC MIANALYZE DATA=MIXEDLSMEANS1;
ODS OUTPUT PARAMETERESTIMATES=GROUP OUTPUT;
BY TRTP;
MODELEFFECTS ESTIMATE;
```

```
STDERR STDERR;
RUN;

PROC MIANALYZE DATA=DIFF1;
    ODS OUTPUT PARAMETERESTIMATES=GROUP_OUTPUT;
    BY comparison;
    MODELEFFECTS ESTIMATE;

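### The Week 56 SHS extrapolation inflates the placebo variance about 5.4-fold, and the equal-variance ANCOVA applied to it gives wrong intervals for at least the individual arms unless progression is linear

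*SAP*

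**What the plan says.** SAP 9.2.4 (Radiographic Endpoints) sets the Week 56 rule. For placebo subjects who moved to upadacitinib at Week 24, "their Week 56 x-ray data will be imputed via linear extrapolation using Week 24 x-ray data". Under the design (SAP 4.2, Figure 1 footnote c) every placebo subject switches at Week 24 whatever the response, so the rule covers all placebo subjects who remain on treatment. Subjects in the active arms keep their observed Week 56 film unless it is missing.

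On inference, the same section says: "Similar statistical inference approach as Week 24 analysis by original randomized treatment group will be used". For continuous SHS, the Week 24 method is in SAP 9.2.3: "For change from baseline in SHS at Week 24, statistical inference will be conducted using ANCOVA model and the associated data handling", with treatment, current DMARD use and baseline as model terms, and an LS mean with 95% CI for each randomized group as well as for each difference.

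The only radiographic ANCOVA code is in Appendix D: "MODEL CHG = BASELINE TRTP STRATA / SOLUTION". It has one residual variance, no GROUP= or EMPIRICAL option, and no restriction to two arms. Earlier in the same appendix, the tipping-point analysis for non-radiographic endpoints uses "ANCOVA analysis with Huber-White sandwich errors". The CMH code in Appendix A is explicitly limited to two arms.

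On the status of the Week 56 results, SAP 9.2.4 states: "Nominal p-values will be provided".

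**The concern.** The extrapolation rule makes the placebo arm more variable than its own Week 24 data by a known factor. The model then assumes that all arms share one variance. If that variance is estimated over all four arms, the three less variable active arms pull it down, and the standard error for upadacitinib versus placebo is too small. Whatever arms are pooled, the interval around each arm's own mean uses a variance that does not belong to that arm.

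Prevention of structural progression versus placebo is a stated secondary objective. The extrapolated analysis is the only Week 56 analysis that tries to compare upadacitinib with continued placebo, so readers will look to its intervals.

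**Working it through.** **Inputs.** Planned size is 410 per upadacitinib dose, 410 on adalimumab, and 205 + 205 = 410 on combined placebo (SAP 4.2). The reported CI level is 95% (SAP 9.2.3). No SHS variance is given for any arm or visit.

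**The plan's own SHS figure (SAP 4.3).** Effect size 0.26, two-sided alpha 0.025, 10% dropout: n = 410 x 0.9 = 369 per arm. Power = Phi(0.26 x sqrt(369/2) - 2.241) = Phi(1.29) = 90.2%. The stated 90% is reproduced. It concerns Week 24 and does not bear on the Week 56 rule.

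**Variance multiplier.** On nominal weeks, 56/24 = 2.333, and squared this is 5.44. Films are taken at Screening, and the SAP does not say whether actual dates are used. With a film at Day -35 the factor is (392 + 35)/(168 + 35) = 427/203 = 2.10, and squared 4.42.

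**Assumption.** Let g be active-arm Week 56 variance divided by placebo Week 24 variance. It is not in the documents. It is varied from 1 (no added spread after Week 24) to 5.44 (each subject progresses linearly, with Week 24 variances equal across arms). Values outside that range would move the results beyond those shown.

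**All-arm model.** Pooled variance = (3g + 5.44)/4. SE ratio (model/true) = sqrt[2 x pooled/(g + 5.44)]. Type I error = 2[1 - Phi(1.96 x ratio)].

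| g | Pooled variance | SE ratio | Type I error |
|---|---|---|---|
| 1 | 2.11 | 0.809 | 11.3% |
| 1.5 | 2.49 | 0.846 | 9.7% |
| 2.33 (grows with time) | 3.11 | 0.894 | 8.0% |
| 3 | 3.61 | 0.925 | 7.0% |
| 4 | 4.36 | 0.961 | 6.0% |
| 5.44 (linear) | 5.44 | 1.000 | 5.0% |

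An ANCOVA simulation (410 per arm, baseline and stratum covariates, 8,000 runs) gave 11.4%, 7.3% and 5.0% at g = 1, 2.33 and 5.44. The Monte Carlo standard error at 8.0% is sqrt(0.08 x 0.92/8000) = 0.3 points, so 7.3% is slightly more than two standard errors low; the formula value is kept.

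Two variations:
- With the actual-date factor of 4.42, type I error is 10.5% at g = 1 and 6.2% at g = 3.
- If 10% of subjects in every arm are also extrapolated (assumed: actives from Week 24, placebo dropouts from Week 16), it is 10.3% at g = 1.

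**Pairwise model, 410 versus 410.** Pooled variance = (g + 5.44)/2, and pooled x 2/n = (g + 5.44)/n, which is the true variance of the difference. The SE ratio is 1.00 and type I error 5.0% for every g. With 350 placebo and 380 active subjects at g = 1, the ratio is 0.972 and the error 5.7%.

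**Intervals for each arm's mean.** Width ratio = sqrt(pooled/own variance). Coverage = 2 Phi(1.96 x width ratio) - 1.

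| Model | g | Placebo width ratio | Placebo coverage | Active width ratio |
|---|---|---|---|---|
| Pairwise | 1 | 0.77 | 86.8% | 1.80 |
| Pairwise | 2.33 | 0.85 | 90.2% | 1.29 |
| All-arm | 1 | 0.62 | 77.8% | 1.45 |
| All-arm | 2.33 | 0.76 | 86.2% | 1.15 |

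**The case against.** The strongest reply is that the SAP never says the ANCOVA is fitted to all four arms. SAP 9.2.3 describes each dose against placebo, the Appendix D code is an example for a Week 24 multiple-imputation analysis, and Appendix A works pairwise. On a pairwise reading with equal arms, the test has its nominal size. This stands, and it is why the contrast result has to be conditional. The unrestricted treatment levels in Appendix D and the LS mean for every randomized group still make one model the likelier reading. The pairwise reading does not rescue the per-arm intervals.

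A second reply is that linear progression is the premise of the extrapolation, and under it g reaches 5.44 and nothing is wrong. That also stands as the lower end of the range. It requires equal Week 24 variances, perfectly linear change in every active subject and no reader error. SAP 9.4.25 averages two readers and adjudicates discrepant change scores, so reader error is expected. Extrapolation multiplies it, whereas in an observed change it need not grow with time.

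A third reply points to the safeguards. In the parallel analysis, "In the AO analysis, the observed Week 56 measurements will be used regardless of treatment switching", but those placebo films come after up to 32 weeks on upadacitinib, so that analysis answers a different question. The random coefficient model, whose group option "is used to allow for heterogeneity among treatment groups in the covariance structure", is specified for Week 24 progression. It shows that unequal variance was foreseen, but it does not correct the Week 56 ANCOVA.

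A reader might infer that false positives double in general. That needs both the all-arm model and g near 1, and the documents establish neither. A reader might also extend the size of the problem to the ranked Week 24 SHS test. The documents give no rescue or extrapolation rates by arm, so no magnitude can be supported there.

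**Conclusion.** The point holds in a limited form. The 5.44 multiplier follows from the SAP's rule on nominal weeks, and no unequal-variance model is named for the Week 56 extrapolated ANCOVA. In an all-arm model, type I error for upadacitinib versus placebo at nominal 5% runs from 5.0% to about 11% for g between 1 and 5.44. In a pairwise model with equal arms the contrast is sound, and the error is confined to the per-arm intervals: placebo coverage is about 87% to 90% for g from 1 to 2.33, with active intervals correspondingly too wide. All of this rests on the assumed g and on planned arm sizes.

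It would be wrong to conclude that the trial's error control is compromised. Week 56 SHS is an additional endpoint, outside the ranked list and the graphical procedure. What is at stake is the accuracy of descriptive intervals and nominal p-values on structural progression.

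**What to change.** For the Week 56 linear-extrapolation ANCOVA of SHS, erosion score and joint space narrowing score, fit a residual variance per treatment group (REPEATED / GROUP=TRTP). Alternatively, use the EMPIRICAL option with the subject-level REPEATED statement already in the Appendix D tipping-point code. State whether the model includes all arms or is pairwise, and whether extrapolation uses nominal weeks or actual film dates.

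SAP 11.1 says Period 1 reporting was completed under version 3.0 and that the current version governs only later long-term reporting. SAP 9.1.2 drops linear extrapolation from Week 104 onward. The change is therefore a reanalysis or check of the reported Week 56 intervals, not an edit that would alter a future table. It takes one model option and a sentence of text, needs no new data and leaves the estimand as it is. Unless progression is close to linear, placebo intervals will widen and active intervals will narrow. In an all-arm model, the upadacitinib-placebo interval will widen too.
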